7.4. Measures Taken to Minimize/Avoid Bias

7.4.1. Randomization (Day 1)

If eligible for the study, patients will be randomized in an approximate 1:1 ratio to have the skin at the surgical site scrubbed with the [REDACTED] or [REDACTED] applicator. A

stratified permuted block randomization procedure will be performed via an interactive web-based randomization system (IWRS) with type of surgery [clean (class I wound) or clean-contaminated (class II wounds) surgery]) as the stratification variable.

If the patient is randomized and is never treated with one of the investigational products or never underwent surgery, then the patient will be considered a randomization failure and an additional patient will be randomized with the next randomization sequence at the time he/she is randomized. The reason(s) that a patient was considered a randomization failure or screen failure will be documented in source documents and eCRFs.

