6.2. Investigational Product Labeling and Storage

Zurex will label, package and provide the [REDACTED] Applicator to the study site. The [REDACTED]. The applicators should be stored as per labeling at 15 to 30°C (59 to 86°F). The product supplies will be provided in their regular packaging. An example of the [REDACTED] label is shown in Figure 1.

Figure 1: Example of [REDACTED] Applicator Label

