11.2. Analysis Sets

The full analysis set includes all patients who were randomized to study treatment, received the study treatment, and underwent surgery. The per-protocol (PP) subset includes all full analysis set patients who had final follow-up at 30 days post-surgery. The safety subset will include all patients who were randomized to the study and received a study treatment and will be analyzed as they were treated. All analyses will be performed for each analysis set.

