4. DEFINITION OF ANALYSIS SETS

The study analysis populations will consist of the following:

Full Analysis Set [modified intention-to-treat (mITT) analysis set]: The mITT analysis set includes all patients who were randomized to study treatment, received the study treatment, and underwent surgery. Subjects will be analyzed by treatment received, not treatment randomized.

Safety Analysis Set: This is all patients that received study treatment. Patients are assigned to the treatment given, not randomized. If this set is different from mITT then it will be used in analysis and listings for adverse events

Per Protocol Analysis Set: The per-protocol (PP) subset includes all full analysis set patients who had final follow-up at 30 days post-surgery.

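### The SAP groups the efficacy set by product received, and operated patients given neither product drop out of every set, so no SSI analysis keeps the randomized comparison

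*Protocol*

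**What the plan says.** **Who is replaced.** Protocol 7.4.1 covers a randomized patient who "is never treated with one of the investigational products or never underwent surgery". In that case "the patient will be considered a randomization failure and an additional patient will be randomized", using the next entry in the randomization sequence. The reason is to be documented.

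**Who is analysed.** Protocol 11.2: "The full analysis set includes all patients who were randomized to study treatment, received the study treatment, and underwent surgery". SAP section 4 sets the same three conditions and calls the set mITT. The other two sets are no wider for an operated patient:
- Per-protocol: "The per-protocol (PP) subset includes all full analysis set patients who had final follow-up at 30 days post-surgery".
- Safety: "The safety subset will include all patients who were randomized to the study and received a study treatment" in the protocol and "This is all patients that received study treatment" in the SAP.

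**In which arm.** Protocol 11.2 specifies analysis as treated for the safety subset only and says nothing of the kind for the full analysis set. SAP section 4 says of the full analysis set: "Subjects will be analyzed by treatment received, not treatment randomized".

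**Knowledge of the arm.** Protocol 7.4, on avoiding bias, covers only randomization and preoperative instructions. Protocol 6.2 adds: "The product supplies will be provided in their regular packaging". Protocol 10.3 puts randomization on the day of surgery, after the eligibility check. The instruction in Protocol 7.10 not to withdraw patients applies only after the product has been used.

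**The concern.** Two rules loosen the link between the arm assigned and the SSI rate reported.

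The first is grouping by product received. The comparator is the standard of care, so a team reluctant to use the new product on a particular patient would most naturally turn to the comparator. Under the SAP, that patient and any later SSI count in the comparator arm. The per-protocol set is drawn from the same set, so it offers no as-randomized view either.

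The second is exclusion. Because the failure rule is triggered by no study product or no surgery, it also catches a patient who had surgery after some other skin preparation. That patient can have an SSI within 30 days of surgery, yet belongs to no analysis set.

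If either event depends on both the assignment and the patient's risk, the arms are no longer comparable. The stated efficacy objective concerns SSI rates under two randomized products, and stratified randomization was chosen to make the arms alike. Sampling error can be judged from the reported counts, whereas this kind of selection cannot.

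**Working it through.** **Step 1: set membership, from Protocol 7.4.1 and 11.2 and SAP section 4**

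| Randomized patient | Replaced | Full / mITT | PP (if Day 30 reached) | Safety | Arm for SSI |
|---|---|---|---|---|---|
| Assigned product, surgery | no | yes | yes | yes | assigned |
| Other study product, surgery | no | yes | yes | yes | the other arm |
| Neither product, surgery | yes | no | no | no | none |
| No surgery, no product | yes | no | no | no | endpoint cannot occur |

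The second and third rows are the problem. The fourth is harmless, because the endpoint is defined from surgery.

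**Step 2: inputs**
- 100 patients per arm (SAP section 6, a convenience sample; there is no alpha, power or effect size to reproduce).
- Base SSI risk of 5%: an assumption, at the lower end of the class II range of 5-15% in Protocol Appendix A.
- 5 higher-risk patients per arm at 15% to 30%: assumptions. The upper value exceeds the Appendix A ranges but lies within the 3% to 45% that the protocol's Introduction reports from the literature.
- No product effect.

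**Step 3: crossover.** Each arm is randomized with 95 patients at 5% and 5 at risk q, so both have the same true rate:
- q = 15%: (95 × 0.05 + 5 × 0.15)/100 = 5.50%.
- q = 30%: (95 × 0.05 + 5 × 0.30)/100 = 6.25%.

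Move one arm's 5 to the other, as grouping by product received would do:
- Arm that loses them: 95 × 0.05/95 = 5.0%.
- Arm that gains them, q = 15%: (95 × 0.05 + 10 × 0.15)/105 = 6.25/105 = 5.95%.
- Arm that gains them, q = 30%: (95 × 0.05 + 10 × 0.30)/105 = 7.75/105 = 7.38%.

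The false gap is 0.95 to 2.38 percentage points.

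**Step 4: exclusion.** 100 patients are retained at 5%, and 5 operated patients are dropped from that arm:
- q = 15%: (100 × 0.05 + 5 × 0.15)/105 = 5.48%.
- q = 30%: (100 × 0.05 + 5 × 0.30)/105 = 6.19%.

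The reported 5.0% is too low by about 0.5 to 1.2 points. Without any assumption on q, 5 SSIs in 100 with 5 dropped patients is compatible with anything from 5/105 = 4.8% to 10/105 = 9.5%.

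**Step 5: yardstick.** The exact 95% interval for 5/100 is 1.6% to 11.3%. The standard error of a difference between two arms of 100 at 5% is √(2 × 0.05 × 0.95/100) = 3.1 points. The shifts in Steps 3 and 4 are below one standard error.

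**The case against.** The strongest reply is that the mechanism is conjecture. No passage describes a team changing the product. Eligibility, including allergy, is rechecked on the day of surgery before randomization, and the application steps in Protocol 6.3 are nearly the same for both products. The SAP plans no hypothesis test, and no decision rule rests on the full analysis set. These points stand and they limit the severity. They do not explain why the SAP's efficacy grouping goes beyond the protocol's as-treated clause.

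A reader might infer more than the documents support in three ways:
- *That replacement conceals the losses by restoring 100 per arm.* It does not. The additional patient takes the next sequence entry and may fall in either arm. If 5 were lost from one arm and replaced, the expected split would be about 97.5 v 102.5. Reasons are recorded, the disposition form covers everyone randomized, and SAP Table 1 tabulates disposition for all randomized subjects. What these records do not provide is an SSI analysis that includes the lost patients.
- *That a patient switched to the standard product is dropped.* That patient received a study product, so stays in the set under the other arm. Only a patient given neither product is dropped, which is probably the rarer event.
- *That the trial is declared open-label.* The available text does not say so. Lack of masking is inferred from the absence of any masking measure and from the regular packaging.

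**Conclusion.** The point holds, with modest severity. SAP section 4 applies as-treated grouping to the efficacy set where Protocol 11.2 applies it only to safety. Separately, operated patients who received neither product are outside every analysis set although they can have the primary endpoint. As a result, no planned SSI analysis set follows the randomization.

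The set logic rests on the text alone. The sizes, a false gap of about 1.0 to 2.4 points from crossover and an understatement of about 0.5 to 1.2 points from exclusion, rest on assumed counts and risks. They would be zero if every patient received the assigned product, and near zero if departures were unrelated to risk and there were no product effect. The documents give no expected number of crossovers or failures and do not say that failures are followed for SSI to Day 30. The case for a change is that the randomized comparison can be kept at little cost, not that a large bias has been shown.

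**What to change.** In Protocol 11.2 and SAP section 4:
- Define the full analysis set for SSI as all randomized patients who underwent surgery, analysed in the arm assigned whatever skin product was used.
- Follow all of them for SSI to Day 30, including those given neither study product.
- Keep the present treated set, grouped by product received, as a supportive SSI analysis and for safety.

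In Protocol 7.4.1, limit exclusion and replacement to patients who had no surgery. In SAP Table 1, make sure that randomization failures appear by arm and reason; the table shell is not in the available text, so this may already be planned.

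The cost is a protocol amendment, which under Protocol 13.2.1 needs sponsor and IRB approval and submission to FDA, matching SAP wording, and inpatient and telephone follow-up of probably a few more patients. The statistical price is slight dilution of any product difference by patients not given their assigned product; the supportive treated analysis shows how much that matters.

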7.4.2. Preoperative Surgical Instructions

Each patient undergoing surgery at the MCW is instructed to shower with an antiseptic agent before the day of surgery. Additionally, the surgical staff follows standard preoperative surgical orders while prepping the patient for surgery. The patient will be asked about adherence to the instructions before surgery and the source documents will be checked for adherence to the standard preoperative surgical orders / activities the day of surgery.

7.5. Interventions (Day 1)

Patients will have the region surrounding the surgical site scrubbed with the assigned product as described in section 6.3.

7.6. Assessments During the Inpatient Period

During the post-surgical period while the patient is still in the hospital, the surgical site and surrounding area will be examined for signs of infection or other deep incisional infection and if evident, this will be recorded. Local skin reactions (erythema, rash, or pruritus) or other systemic allergic reactions to the investigational product will be recorded. Other AEs will be assessed by asking the patient an open ended question: How are you feeling? If any antibiotics are prescribed for prophylaxis or treatment of an AE, these will be reported. On the day of hospital discharge, all of the above assessments will also be performed. The patient will be given standard discharge instructions and a card with the name of study nurse or doctor to contact in the event of any post-surgical complications. Patients will be scheduled for an examination appointment or possibly to come to the emergency room if any possibly serious complications have occurred.

7.7. Assessments During the Outpatient Period

If an outpatient follow-up visit has been scheduled, a physical examination should be performed including inspection of the surgical site for signs of an SSI and the skin at the application site for signs of an allergic reaction and new antibiotic prescriptions. Other AEs should be assessed with an open ended question and data will be recorded.

7.8. Telephone Assessments

Three-to-five days after hospital release, on study Day 30 or at any time a patient calls with a complaint, a telephone scripted interview will be completed that assesses AEs and the patient should be queried if they had any other doctor's office visits that might be indicative of a post-surgical problem indicative of an SSI or AE. If the patient cannot be contacted at Day 30, a person that they listed on the locator form should be called to determine if the patient died or is

otherwise hospitalized or to the best of their knowledge has had no medical issues requiring hospitalization, emergency care, or other doctor's office visit. Also, if the patient cannot be contacted on Day 30, it is permissible to continue to try to reach the patient up to 7 days later to collect the data on the scripted interview reminding the patient that the data is only for the period up to Day 30.

7.9. Duration of Patient Participation

Each patient will participate in the study for up to 51 days including up to 21-days after consenting to the study for screening up to the day of surgery and a Day 30 post-surgical follow-up telephone call or visit (if needed) to determine if there is any evidence of an SSI or other AE.

7.10. Patient Withdrawal or Discontinuation Procedures

Each patient has the right to withdraw consent and withdraw from the study at any time. As each patient receives a single study treatment over the course of a few minutes, once the patient has received a treatment, the investigator should not withdraw the patient from the study and should try to complete all safety follow-up assessments including examinations for SSIs.

In the event that a patient withdraws, the reason(s) for the discontinuation from the study will be recorded. At the time that the patient withdraws, he/she should be asked to complete the safety assessments in accordance with the schedule in [Table 3](#), if possible.

7.11. Study Termination Criteria

Zurex or the Investigator has the right to discontinue the study at any time for medical and/or administrative reasons. As far as possible, this should occur after mutual consultation.

7.12. Product Evaluation Survey

8. Study Endpoints

8.1. Efficacy Endpoints

8.1.1. Primary Efficacy Endpoint

The primary efficacy endpoint is the occurrence of any SSI within 30 days after surgery.

A secondary analysis of the primary efficacy endpoint include subgroup analyses as follows:

- SSI rates by different types of SSI classified as superficial incisional infection (which involves only skin and subcutaneous tissue and excludes stitch related abscesses),

deep incisional infection (which involves fascia and muscle), or organ-space infection (which involves any organ or space other than the incised layer of body wall that was opened or manipulated during the operation) (definitions in accordance with [CDC-2019](#) will be used).

- SSI rates by type of surgery including clean (class I wound) or clean-contaminated (class II wounds) surgeries

8.2. Safety Endpoints

Safety endpoints will be analyzed over the entire treatment and follow-up period.

- AEs (including specifically local application site reactions and allergic reactions)

9. Safety Monitoring Plan

Safety monitoring will be conducted throughout the study; therefore safety concerns will be identified by continuous review of the data by the PI, clinic staff, clinical monitor, medical monitor, and Zurex.

The IRB, Medical Monitor, PI, Clinical Monitors and Zurex will review any safety concerns throughout the trial. The roles of these individuals are described below.

Medical Monitor: A Medical Monitor has been appointed for the study. The Medical Monitor will be available for making recommendations to the investigator and Zurex on the severity of any SAEs, and the relatedness to the study interventions. The Medical Monitor will also be responsible for tracking and assessing trends in the AEs reported.

Clinical Monitors: The PI will allow representatives of Zurex to periodically monitor, at mutually convenient times during and after the study, all study data. These monitoring visits provide Zurex with the opportunity to evaluate the progress of the study and to obtain information about potential problems. The monitors will assure that submitted data are accurate and in agreement with any medical records or paper source documentation used; verify that investigational products are properly stored and accounted for, verify that patients' consent for study participation has been properly obtained and documented, confirm that research subjects entered into the study meet inclusion and exclusion criteria, and assure that all essential documentation required by Good Clinical Practices (GCP) guidelines are appropriately filed.

Monitors will conduct a site initiation visit prior to the start of the study. At this visit, they will assure that proper study-related documentation exists, assist in training investigators and other site personnel in study procedures and GCP guidelines, confirm receipt of study supplies, and assure that acceptable facilities are available to conduct the study.

Routine monitoring visits by Zurex's representatives will be scheduled at appropriate intervals but more frequently at the beginning of the study. At these visits, the monitors will verify that study procedures are being conducted according to the protocol guidelines, monitor eCRFs against source documents, review AEs and SAEs, and perform drug accountability. At the end of the study, they will confirm that the site has the appropriate essential documents on file, advise on storage of study records, and inspect the return and destruction records for unused investigational products.

10. Assessment Methods

All study assessments will be performed at the time points outlined in the Schedule of Assessments ([Table 3](#)) that is somewhat flexible due to different lengths of hospitalization after surgery and depending on the needs of the patient. The following sections outline the details and procedures associated with the assessments. All specified assessments will be recorded on a source document or the medical record and appropriate data will be transcribed into electronic case report forms (eCRFs).

10.1. Adverse Events and Serious Adverse Events

The investigator and study site staff are responsible for the detection, documentation, classification, reporting, and follow up of events meeting the definition of an AE or SAE.

10.1.1. Adverse Event Definition

An AE is any untoward medical occurrence in a patient or clinical investigation subject administered a pharmaceutical product and may not necessarily have a causal relationship with the administered treatment. An AE can therefore be any unfavorable and unintended sign (including a clinically significant laboratory abnormality), symptom, or disease temporally associated with the use of an investigational product, whether or not related to the investigational product. Pre-existing conditions, diseases, or disorders are not considered AEs unless there is a change in severity or frequency. Planned surgeries will not be considered an AE.

10.1.2. Serious Adverse Events and Serious Unexpected Adverse Events Definition

An SAE is any untoward medical occurrence that meets one of the following:

- Results in death
- Is life-threatening (at the time of the event)
- Requires inpatient hospitalization or prolongation of existing hospitalization
- Results in persistent or significant disability/incapacity
- Is a congenital anomaly/birth defect

A serious and unexpected AE is an SAE that is not identified in nature, intensity, or frequency in the risk information included in the Product Label for the drug.

Important medical events that may not result in death, be life-threatening, or require hospitalization may be considered a serious adverse drug experience when, based upon appropriate medical judgment, they may jeopardize the study patient and may require medical or surgical intervention to prevent one of the outcomes listed in the definition.

10.1.3. Methods/Timing for Assessing, Recording, and Analyzing Safety Endpoints

AEs will be assessed starting after the first administration of investigational product until the final follow-up at Day 30. General symptoms will be collected via an open ended question: How have you been feeling since the last time we spoke? Elicited AEs will be assessed as described in section [10.1.4](#).

AEs will be documented in the medical/source records, and recorded on the eCRF using accepted medical terms and/or the diagnoses that accurately characterize the event. When a diagnosis is known, the AE term recorded on the eCRF will be the diagnosis rather than a constellation of symptoms. The investigator will assess all AEs for seriousness, relationship to investigational product, and severity. When an event has not resolved by study closure, it will be documented on the AE CRF as “ongoing”.

All AEs, including clinically significant abnormal findings on laboratory evaluations, regardless of severity, will be followed by study physicians until satisfactory resolution (the event either resolved or stabilized and is not expected to resolve in the near term). At the follow-up telephone contact, AEs will be recorded and followed to resolution only if they are serious, or if the study physician assesses them to be clinically significant.

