3.4. Safety of

All components in [REDACTED] solution are either noted within the FDA's Inactive Ingredients Database as safe or have a long history of safe and effective use. The safety of [REDACTED] Isopropyl Alcohol (70% v/v) Solution was demonstrated in the clinical program. Across the

[REDACTED]

4. Study Objectives

The primary efficacy objective of this study is to determine the efficacy of two skin preparation products, [REDACTED] Applicator and a standard of care [REDACTED] Applicator ([REDACTED]) on the rates of SSI.

The primary safety objectives are to determine the rates of skin irritation or allergic reactions attributed to each product and all other AEs.

5. Investigational Plan

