This study is a 2-arm, randomized, parallel group, single-site study designed to determine the SSI rates within 30-days post-surgery of pre-surgical skin cleansing with [REDACTED] Applicator or [REDACTED] on patients who are planning to undergo clean (class I wound) or clean-contaminated (class II wounds) surgery based on medical chart review will be approached to consent for the study (see [Appendix A](#) for wound classification definitions and types of surgical procedures to be included). After consenting to the study, screening will be conducted to determine patient eligibility. Eligibility will be determined from chart review and conducting any procedures for information not in the medical chart (e.g., signs of infection at the surgical site where an incision will be performed or patient reported allergies to components of the surgical scrubs). Pre-operative data to be collected on electronic case report forms (eCRFs) include patient's demographics, medical history, antibiotics in the last 4 days, and record of planned surgery. Eligible patients will be randomized with stratification by type of surgery (clean versus clean-contaminated) in a 1:1 ratio to receive skin pretreatment with either [REDACTED] Applicator or [REDACTED] and will undergo surgery. A total of 200 patients is planned (100 in each group). The surgical site will be examined for signs of infection and local skin reactions at least once a day during hospitalization, and at discharge. The patient will be contacted by telephone approximately 3-to-5 days post hospital release and at 30-days post the day of surgery. During these telephone contacts, the patient will be asked about signs of local skin or systemic allergic reactions and a general question about how they are feeling to determine if any other AEs may have occurred. If during these queries, the patient reveals any events that may be indicative of an SSI, they will be asked to see a study doctor to determine if an SSI has occurred. If they have visited another doctor for an evaluation, the patient will be asked to provide any relevant medical records to include in the study files. At any time after discharge up to 30 days post-surgery, the patient will be encouraged to call a study nurse or doctor and arrange for a prompt clinical evaluation if an infection is suspected. Study assessments and procedures will be performed as outlined in the Schedule of Assessments ([Table 3](#)).

Table 3: Schedule of Assessments

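### As worded, Protocol 10.1.3 restricts the recording, not only the follow-up, of adverse events reported by telephone, so non-serious skin reactions could be missing from the primary safety rates

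*Protocol*

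**What the plan says.** Protocol section 10.1.3 contains four statements that bear on this point:

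- Window: "AEs will be assessed starting after the first administration of investigational product until the final follow-up at Day 30". The Day 30 follow-up is itself a telephone call.
- Recording: "AEs will be documented in the medical/source records, and recorded on the eCRF", with no condition on seriousness or significance.
- Follow-up in general: all AEs, "regardless of severity, will be followed by study physicians until satisfactory resolution".
- Events reported by phone: "AEs will be recorded and followed to resolution only if they are serious". The sentence goes on to admit events that a study physician judges clinically significant.

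Elsewhere, Protocol section 4 states the aim: "The primary safety objectives are to determine the rates of skin irritation or allergic reactions attributed to each product and all other AEs". Section 8.2 has safety analysed over the whole treatment and follow-up period. On the calls, section 5 says that "the patient will be asked about signs of local skin or systemic allergic reactions", and section 7.8 says that "a telephone scripted interview will be completed that assesses AEs". Table 3 marks open-ended and elicited AE questions in both telephone columns. Section 10.1.4 lets erythema, rash and pruritus be assessed by examination or by asking the patient, and Table 4 gives each of them a mild grade.

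SAP section 8.6.1 tabulates elicited AEs separately by arm, and the shell for SAP Table 20 shows them by maximum severity. Neither mentions a restriction for events reported by telephone.

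**The concern.** In the telephone sentence one condition follows two joined verbs, record and follow. Read as it stands, an itch or rash that a patient mentions on the call is entered only if it is serious or a physician considers it clinically significant. A site that follows the text would ask the question and then leave a non-serious answer off the eCRF.

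The rates of these reactions are a primary safety objective, and Grade 1 reactions are the ones such a condition is most likely to remove. After discharge, an examination takes place only if an outpatient visit is scheduled (Protocol section 7.7) or the patient comes in with a complaint. For some patients the calls may therefore be the only routine source. SAP section 7 takes all study data from the eCRFs, so an event not entered there cannot reach the tables, and the tables would give no sign that it was missing.

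**Working it through.** The plan gives no figure to reproduce. The study is descriptive (SAP section 5) and the sample of 200 is one of convenience (SAP section 6). The check is a comparison of texts.

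1. **Within Protocol 10.1.3.** The recording paragraph has no condition. The last sentence of the next paragraph puts one on recording at the telephone contact. Taken literally, the two cannot both hold for a non-serious event reported by telephone and not judged significant.
2. **Against the objective and the analysis period.** Section 4 asks for the rates of skin irritation, allergic reactions and all other AEs. Section 8.2 covers the whole follow-up. A rate that omits non-serious events from one mode of contact is not that rate.
3. **Against the SAP.** Section 8.6.1 and Table 20 present elicited AEs by arm and by maximum severity with no restriction. They presuppose that every grade has been recorded throughout.
4. **Against the other contacts.** Sections 7.6 (inpatient) and 7.7 (outpatient) have findings recorded without restriction. Only the telephone contact carries one.
5. **Against the call procedures.** Sections 5 and 7.8 and Table 3 speak of asking and assessing, not of recording. They do not contradict the sentence outright. It undercuts them, because answers are sought and may then not be kept.
6. **Scope.** The sentence refers to one telephone contact, whereas Table 3 schedules two, at 3 to 5 days after release and at Day 30. Section 10.1.7.1 calls the last one the final follow-up call, a term that 10.1.3 does not use for the contact in question. The text does not settle which call is meant.

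**Size, as illustration only.** With 100 patients per arm, one patient whose only occurrence of a reaction goes unrecorded lowers that arm's rate by 1/100 = 1 percentage point. SAP 8.6.1 counts each preferred term once per patient, so a patient already counted for that term costs nothing. More generally:

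recorded rate = true rate × (1 − share lost)

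The share lost is the share of affected patients whose reaction is reported only by telephone and judged neither serious nor clinically significant. The documents give neither quantity. Under assumed values:

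- True rate 5%: share lost 0 gives 5%; 25% gives 5 × 0.75 = 3.75%; 75% gives 5 × 0.25 = 1.25%.
- True rate 10%: share lost 0 gives 10%; 25% gives 10 × 0.75 = 7.5%; 75% gives 10 × 0.25 = 2.5%.

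The understatement therefore runs from 0 to 3.75 points in the first case and from 0 to 7.5 points in the second. These figures show how the effect scales and are not an estimate of it.

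**The case against.** The strongest reply is that the sentence was meant to limit follow-up only. It closes a paragraph about following events to resolution, while recording has its own paragraph with no condition. Protocol section 10.1.6 has an outcome category for events still ongoing at the end of the reporting period or needing no further follow-up, so events that are recorded but not followed are foreseen. Elicited reactions also have their own section, grading scale and SAP table, which makes it less likely that anyone intended to discard the mild ones. On this reading the conflict with the general follow-up rule is an ordinary exception for events met late.

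That reading is plausible and may be the intended one, but it is not what the sentence says. The provisions on elicited reactions do not exempt them from it. The outcome category also shows that recording need not be tied to follow-up at all.

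Other parts of the reply stand and limit the point. If only the Day 30 call is meant, the 3-to-5-day call is unaffected. Daily inpatient checks, the discharge examination and any outpatient or unscheduled visit carry no restriction, so the loss would not be total. No test or margin depends on these rates.

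**Conclusion.** The point holds as a defect of wording with a possible consequence for a primary safety rate. As written, the condition reaches recording, and that conflicts with the recording rule in the same section, the safety objective, the analysis period and the SAP tables. If sites apply it literally, both arms' rates are understated. If they record everything, nothing is lost. The documents do not allow the amount to be estimated.

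A reader might infer more than this:

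- **That mild reactions will be dropped at every call.** The text allows a follow-up-only reading and may concern a single call.
- **That a particular fraction, such as a quarter, is lost.** This needs assumed shares for post-discharge onset and for non-significance, and the documents give neither. The hypersensitivity figures of 1.9% to 3.2% in Protocol section 3.1 are not a benchmark. They concern chlorhexidine hypersensitivity in a separate sample, and exclusion criterion 5 removes patients with a known allergy.
- **That most reactions are mild, or that the calls are the main source after discharge.** Neither is stated, and the number of outpatient visits is not given.
- **That recording will differ between the arms.** The visible text describes no masking, but it does not say who knows the assignment when significance is judged. The condition applies equally to both arms. A distorted comparison would need a difference between arms in the timing of reactions or in the judgement, and nothing in the documents shows one.

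**What to change.** Separate recording from follow-up in Protocol section 10.1.3. State that all AEs and elicited application site reactions reported at any telephone contact up to Day 30 are recorded on the eCRF.

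The two follow-up sentences then need to be reconciled by the sponsor, who should state which contact or contacts the existing condition on seriousness or clinical significance applies to. What that follow-up rule should be is for the sponsor to decide.

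The cost is one added sentence, a clarification of the follow-up text and a note in the site instructions, with the IRB approval that section 13.2.1 requires for an amendment. The SAP tables need no change. If calls have already been made, the completed scripted interviews can be compared with the eCRF entries. A reaction that was never written down may not be recoverable.
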